5.2. Interleukin-12 and Cancer Immunotherapy

Interleukin-12 (IL-12) is a pro inflammatory cytokine and has been recognized as a master regulator of cell mediated immunity in response to intracellular pathogens and neoplastic transformation. Structurally, IL-12 is a heterodimeric protein composed of p35 and p40 subunits covalently linked to form the biologically active IL-12p70 molecule (Carra, Gerosa et al. 2000). IL-12 is produced by innate immune cells in response to pathogens, leading to the production of interferon-gamma (IFN- γ) and tumor necrosis factor-alpha from T and natural killer (NK) cells (Micallef, Ohtsuki et al. 1996, Trinchieri 2003). The discovery that IL-12 can drive naïve T helper cell differentiation to the inflammatory T helper cell type 1 (Th1) phenotype (Hsieh, Macatonia et al. 1993) established IL-12 as a bridge between innate immune cells and the adaptive immune response through polarization of naïve cluster of differentiation (CD) CD4+ cells. IL-12 also directly influences CD8+ T cell differentiation (Kalinski, Hilkens et al. 1999, Curtsinger, Lins et al. 2003) and the reactivation and survival of memory CD4+ T cells (Yoo, Cho et al. 2002). This is particularly important in the context of the tumor microenvironment, where high levels of IL-12 repolarize antigen-experienced CD4+ T cells back to the functional antitumor Th1 phenotype (Wesa, Kalinski et al. 2007).

The first human study of IL-12 as an anticancer agent was a Phase I dose escalation of intravenously (IV) administered recombinant human IL-12 (rhIL-12) in subjects with either melanoma or renal cell carcinoma. There was a transient complete response in melanoma and a partial response in renal cell carcinoma with significant toxicities. The Phase II trial observed similar toxicities, and 2 IL-12-related deaths prompted the Food and Drug Administration (FDA) to suspend the trial (Atkins, Robertson et al. 1997, Leonard, Sherman et al. 1997). Additional studies confirmed that systemic administration of recombinant IL-12 resulted in significant toxicity, limiting its potential for clinical development (Salem, Gillanders et al. 2006). These results prompted the investigation of local (intratumoral) delivery of IL-12 as a direct anticancer therapeutic or as an adjuvant to vaccination.

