7.3. Dose Escalation, Cohort Expansion, and De-Escalation Decision Rules

Expansion cohort(s) are prospectively planned in this study, in Arm 2, at the discretion of the SRC.

Each subject in each dose escalation cohort (3+3 standard design) will be monitored for 28 days before subsequent subjects are enrolled. The SRC will convene after the third and/or final subject in each cohort completes the 28-day DLT evaluation period and will make a recommendation regarding expanding the current cohort by up to 30 additional subjects (phase II component), opening of the next cohort/dose escalating, dose de-escalating, or discontinuing the investigation.

If the SRC recommends expanding the current cohort, a 28-day review period may not be required between each patient. Based on the safety profile of the current cohort, the SRC will make a determination related to the waiting period.

The SRC will determine if/when the MTD is met and may recommend cohort expansion at that dose.

Study stopping rules will be followed as defined in [Section 7.10](#).

Dose Escalation/Cohort Expansion

Each subject in each dose escalation cohort (3+3 standard design) will be monitored for 28 days before subsequent subjects are enrolled. The SRC will convene after the final subject in Cohort 1 completes the 28-day DLT evaluation period. The SRC will make a recommendation regarding:

- Opening enrollment of Cohort 3
- Discontinuing the investigation

If the SRC recommends opening enrollment in Cohort 3, each subject will be monitored for 28 days before subsequent subjects are enrolled in the same cohort. The SRC will convene once the third and/or final subjects (*i.e.*.. subject 3 of 3 or 6 of 6) in Cohort 3 complete the 28-day DLT evaluation period. The SRC will make a recommendation regarding:

- Expansion of Cohort 3 (Phase II portion)
- Opening enrollment of Cohort 4
- Discontinuing the investigation

If the SRC recommends enrollment of Cohort 4, each subject will be monitored for 28 days before subsequent subjects are enrolled in the same cohort. The SRC will convene once the third and/or final subject (*i.e.*, subject 3 of 3 or 6 of 6) in Cohort 4 complete the 28-day DLT evaluation period. The SRC will make a recommendation regarding:

- Expansion of Cohort 4 (Phase II portion)
- Discontinuing the investigation

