7.4. Dose-Limiting Toxicity

An event, occurring within the first 28 days (*i.e.*, Day 0 to Day 28) that meets at least one of the following conditions:

- Any local reaction that requires operative intervention and is felt to be attributable to study drug
- Any local reaction that has life-threatening consequences requiring urgent intervention or results in death and is felt to be attributable to study drug
- Any Grade 3 or higher non-hematologic adverse event that is at least possibly related to study drug and lasts ≥ 3 days
- Nausea and vomiting will not be considered a DLT unless at least Grade 3 or 4 and refractory to antiemetics (*i.e.*, defined as symptoms unrelieved by maximal medical support as directed by the PI (per institutional guidelines) in consultation with the medical monitor).
- Grade 3 or higher thrombocytopenia ($< 50,000/\text{mm}^3$) at least possibly related to study drug

- Any Grade 4 or higher hematologic toxicity (except thrombocytopenia) that is at least possibly related to study drug and lasts ≥ 5 days

Dose escalation may be stopped by the Medical Monitor before a DLT is observed, but where the observed toxicities indicate the strong likelihood of unacceptable toxicity at higher doses.

Note: Diagnostic brain tumor biopsy is not considered a DLT. Seizures, headaches, and cerebral or pontine edema are commonly observed in this population and will be recorded according to the grade of toxicity but will not be considered a DLT unless a relationship to study drug is deemed to be the main contributory factor. Transient neurological changes are expected in Arm 2 and will not be considered a DLT unless they last > 10 days.

Expansion cohorts will be allowed in Arm 2 if deemed appropriate by the SRC. If an expansion cohort is implemented, the veledimex dose may be delayed or reduced for individual subjects in the event of toxicity. If $\geq 33\%$ of subjects in the expansion cohort experience DLTs, using the definition in the dose-escalation phase, additional subjects may be enrolled at the next lower dose tested in the dose-escalation phase or at an intermediate dose, as recommended by the SRC. All DLTs should be reported to the Sponsor within 24 hours of Investigator/site awareness.

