7.10. Study Stopping Rules

In the DLT evaluation period (Day 0 to Day 28), if any subject experiences a local reaction that requires operative intervention and is felt to be attributable to study drug; any local reaction that has life-threatening consequences requiring urgent intervention or results in death and is felt to be attributable to study drug; or any Grade 4 hematologic toxicity, except thrombocytopenia, that is at least possibly related to study drug and lasts \geq 5 days, enrollment of new subjects will be paused pending review by the SRC.

In the event that there are other subjects actively being dosed in the cohort, the treating site's Principal Investigator (PI) and the Medical Monitor will discuss the relationship to study drug and determine whether or not to convene an urgent SRC meeting to make a decision to continue active dosing in ongoing subjects.

The SRC will make a decision to the enrollment of additional subjects at the relevant veledimex dose level, to expand the current dose level cohort, to de-escalate veledimex dosing at the relevant dose level, or to amend the protocol prior to enrollment of additional subjects, or to discontinue enrollment in the study. In the event that a decision is made to de-escalate dosing, the SRC will evaluate the appropriateness of dosing at a previously evaluated lower dose or exploring an intermediate dose level.

For any subject death within 30 days of study therapy, enrollment will be held pending review of the event by the SRC. Active dosing in ongoing subjects will continue at the discretion of the treating site's PI and the Medical Monitor pending the SRC review.

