### 2.2.3. Projection of Study Duration

The study duration is projected to be approximately 48 months. This assumes that after the enrollment and evaluation of cohort 4 for safety, that the SRC recommends expansion of enrollment into the phase 2 single arm cohort of up to 30 to 35 eligible subjects to obtain at least 30 subjects deemed evaluable for OS. The breakdown of timing suggests:

- Arm 2 enrollment of phase I cohorts is approximately 12 months
- 30 to 35 evaluable DIPG subject enrollment begins one month after the SRC recommends expanding enrollment into a phase 2 component.
- Enrollment to accrue Phase II DIPG subjects is projected to be 12 months.
- Then at least 24 months of follow-up of the last subject enrolled and treated as part of the phase 2 projection.

The overall duration is expected to be up to 2 years and 28 days for an individual subject, assuming:

- Screening period of up 28 days
- Study treatment period of up to 15 days
- Survival status through 24 months from the first dosing date.

In addition, subjects who discontinue or complete study treatment without objective evidence of disease progression should continue to be followed until confirmed disease progression has been documented. Subjects will be followed for survival status for 2 years after enrollment. The active study period refers to the study period from informed consent through the Survival Follow-up Period.

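### The enrollment-pause rule in Protocol 7.10 omits two of the five DLT types in 7.4, so in an expansion without the 28-day wait a single non-fatal DLT of those types does not automatically pause enrollment

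*Protocol*

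**What the plan says.** Protocol 7.10, repeated in the synopsis under Safety Evaluation, lists three single-event triggers within Day 0 to Day 28:

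- a local reaction, attributed to study drug, for which an operation is needed
- a local reaction, attributed to study drug, that is fatal or that threatens life and needs urgent treatment
- "any Grade 4 hematologic toxicity, except thrombocytopenia, that is at least possibly related to study drug", when it lasts at least 5 days

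After any of these, "enrollment of new subjects will be paused pending review by the SRC". 7.10 separately holds enrollment for any death within 30 days of study therapy, with no condition on cause.

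Protocol 7.4 defines DLTs more widely. Besides the three types above it counts "Any Grade 3 or higher non-hematologic adverse event that is at least possibly related to study drug and lasts" for 3 days or more, and related Grade 3 or higher thrombocytopenia with no duration test. Its lines on nausea and vomiting and on transient neurological changes limit what counts as a DLT.

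During escalation each subject is observed for 28 days before the next is enrolled (7.3). For the expansion of up to 30 subjects, "a 28-day review period may not be required between each patient"; the SRC decides on the wait from the cohort's safety profile.

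Three further provisions count DLTs of every type:

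- **33% rule.** 7.4 allows enrollment at a lower or intermediate dose once at least 33% of expansion subjects have DLTs. 7.6 requires the SRC to convene at 33%.
- **Two-DLT rule.** After two DLTs in a cohort, the synopsis stops dosing of subjects in that cohort. Section 7.5 and SAP 4.4 stop only dose escalation.
- **Table 6.** The affected subject's drug is held for any drug-related Grade 3 or higher event, apart from nausea or vomiting without optimal antiemetic treatment.

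**The concern.** Safety is the primary endpoint, yet the automatic pause responds to a narrower set of harms than the trial itself calls dose-limiting.

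Platelets show this most clearly. In 7.4 the exception for thrombocytopenia makes sense because platelets have their own, stricter criterion. 7.10 carries over the exception without that criterion, which reverses the order of strictness: related Grade 4 neutropenia lasting 5 days pauses enrollment, while non-fatal Grade 4 thrombocytopenia of any length does not. No reason is given. Elsewhere the protocol treats bleeding as a real risk: 8.1 sets a platelet minimum of 100,000/mm³, 8.2 prohibits systemic heparinization and acetylsalicylic acid during dosing, and 10.1 asks that intracranial bleeding be evaluated before the first post-injection dose.

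The other omission matters because Protocol 5.2 reports that "systemic administration of recombinant IL-12 resulted in significant toxicity". A non-fatal, non-local Grade 3 or 4 non-hematologic DLT is the form in which such toxicity could appear.

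At stake is whether the next child is enrolled in the expansion before anyone is obliged to review such an event.

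**Working it through.** The documents state no operating characteristic for the pause rule, so there is no figure to reproduce. The check is a comparison of text, followed by arithmetic on the exposure and the backstops.

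**1. DLT types in 7.4 against single-event triggers in 7.10**

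| DLT type in 7.4 | Pause in 7.10? |
|---|---|
| Attributable local reaction needing operation | Yes |
| Attributable life-threatening or fatal local reaction | Yes |
| Related Grade 4 or higher hematologic toxicity other than platelets, at least 5 days | Yes (7.10 says Grade 4) |
| Related Grade 3 or higher non-hematologic event, at least 3 days | No, unless also a listed local reaction or a death within 30 days |
| Related Grade 3 or higher thrombocytopenia | No, unless a death within 30 days |

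Three of five types are covered and two are omitted. If the nausea and vomiting bullet is counted as a type of its own, three of six are covered.

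**2. Pace of the expansion**

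SAP 2.2.3 plans 30 to 35 subjects and states: "Enrollment to accrue Phase II DIPG subjects is projected to be 12 months". With even accrual, the number starting in one 28-day DLT window is:

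- 30 / 365.25 × 28 = 2.30
- 35 / 365.25 × 28 = 2.68

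This measures pace. It is not the number a pause would spare, because the documents give no SRC review time.

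**3. The 33% rule**

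Neither 7.4 nor 7.6 gives a denominator or a look schedule. As a running proportion it is met by 1 of 3 (33.3%). Read once at n = 30 it needs 10 subjects with DLTs, since 0.33 × 30 = 9.9. On that single-look reading, which is an assumption, the chance of reaching it is P(X ≥ 10) for X binomial(30, p):

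- assumed true DLT rate p = 0.20: 0.061
- assumed true DLT rate p = 0.30: 0.411

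**4. The two-DLT rule**

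If the synopsis wording governed the expansion, P(X ≥ 2) = 1 − (1 − p)^30 − 30p(1 − p)^29. This is 81.6% at p = 0.10 and 98.9% at p = 0.20, so it would be a strong backstop. Whether it applies is not stated. The two-DLT row of Table 5 gives a subject count of 2 to 6, which fits an escalation cohort. In a full expansion, two DLTs are 2/30 = 6.7%, so the rule would act long before a 33% rule read at the end. On the other side, 7.3 describes the Phase II part as an expansion of Cohort 3 or Cohort 4, so the same-cohort wording could reach it.

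**The case against.** A single-event pause may be deliberately narrower than the DLT definition, and the protocol has other safeguards. The investigator contacts the Medical Monitor daily before each veledimex dose (7.2). DLTs reach the Sponsor within 24 hours. Table 6 holds the affected subject's drug. The SRC must convene at 33%, and ad hoc meetings may be requested. The SRC has to choose both to expand and to waive the wait, and its charter is a separate document that is not available here. Section 5.3.2 also says that local delivery of IL-12 by vector has been well tolerated, unlike the systemic protein.

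Much of this stands, and it rules out several stronger readings that a reader might infer:

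- **That most DLT types are left out.** By count, three of five are covered. The omitted two could be the more frequent, but the documents give no rates.
- **That no systemic Grade 3 or higher event triggers a pause.** Grade 4 non-platelet hematologic toxicity does, and any death within 30 days holds enrollment whatever its cause.
- **That the omitted DLTs have no consequence.** The provisions above apply to them. What is missing is an automatic hold on the next enrollment after one event.
- **That the triggers should run to Day 56 because serious adverse events are collected until then.** A DLT window and a collection window serve different purposes, and the death hold already runs to about Day 44 if dosing ends on Day 14 (14 + 30).

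The objection does not account for the platelet exception. If 7.10 is meant to be narrower, nothing says why non-fatal thrombocytopenia should rank below other hematologic toxicity when 7.4 ranks it above. Reporting duties and discretionary meetings inform a decision to pause; they do not require one.

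**Conclusion.** The point holds in a limited form. Under 7.10, a single non-fatal related Grade 3 or higher thrombocytopenia, or a single non-fatal related Grade 3 or higher non-hematologic DLT that is not a listed local reaction, does not automatically pause enrollment. This matters only in an expansion where the SRC waives the 28-day wait; during escalation the wait covers the gap. The accrual figure of 2.3 to 2.7 subjects rests on the SAP's projection and even enrollment. The 6% and 41% figures rest on one look at n = 30 and on assumed DLT rates, so they show how weak the 33% rule could be, not how it must behave. The two-DLT rule might close most of the gap, but its texts conflict and its reach is not stated.

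This is an inexpensive improvement to patient protection and a genuine inconsistency between sections. It does not make the design unsound. Whether every DLT should pause enrollment is a debatable trade-off that the documents do not settle.

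**What to change.** Reconcile the synopsis (Safety Evaluation and the definition of the recommended Phase II dose) with Protocol 7.3 including Table 5, 7.4, 7.5, 7.6 and 7.10:

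1. Align the 7.10 triggers and their synopsis copy with the 7.4 DLT definition. At minimum, resolve the stranded thrombocytopenia exception, or state why it is intended.
2. State, for each DLT type in 7.4, whether a single event holds expansion enrollment pending SRC review when the 28-day wait is waived.
3. State whether the two-DLT rule governs the expansion, and remove the difference between stopping dosing and stopping escalation. The choice belongs to the sponsor and the SRC.
4. Give the 33% rule a denominator and a look schedule.

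The cost is protocol wording plus some enrollment holds. If every DLT type triggered one, the expected number over 30 subjects would be at most about 30 × 0.10 = 3, 30 × 0.20 = 6 or 30 × 0.30 = 9 at assumed DLT rates of 10%, 20% and 30%. It would be fewer if only some types do. The length of each hold cannot be judged from the documents. No new data flow is needed, because DLTs are already reportable within 24 hours.

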7.11. Principal Investigator

The Principal Investigator (PI) for study reporting purposes will be determined by the time of database lock. The PI will be chosen based on his or her contributions to the study design and/or analysis.

8. SELECTION AND WITHDRAWAL OF SUBJECTS

8.1. Inclusion Criteria

The eligible study population includes pediatric subjects with a) recurrent or refractory supratentorial brain tumors, not in direct continuity with the ventricular system, that are unresponsive to conventional treatment or for which there is no alternative curative therapy (Arm 1) and b) non-disseminated DIPG post prior standard focal radiotherapy and for which a biopsy has previously been obtained (access to results required; access to tissue preferred) (Arm 2).

Inclusion Criteria:

1. Male or female subjects ≤ 21 years-of-age with the demonstrated ability to swallow capsules whole and who are willing to provide access to previously obtained biopsy results
2. Provision of written informed consent and assent, when applicable, for tumor resection, stereotactic surgery, tumor biopsy, sample collection, and/or treatment with study drug prior to undergoing any study-specific procedures
3. **Arm 1:** Evidence of recurrent or progressive supratentorial tumor, which has shown a $> 25\%$ increase in bi-dimensional measurements by MRI or is refractory with significant neuro-deterioration that is not otherwise explained with no known curative therapy, not in direct continuity with the ventricular system (e.g., there is physical separation between the tumor and ventricle, the tumor does not open directly into the ventricular system).
4. **Arm 2:** Clinical presentation of DIPG and compatible MRI with approximately 2/3 of the pons included and without evidence of dissemination. Subjects should be ≥ 2 weeks and ≤ 10 weeks post standard focal radiotherapy (*i.e.*, dose of 5400 to 5960 cGy and maximum dexamethasone of 1 mg/m²/day).
5. At the time of registration, subjects must have recovered from the toxic effects of previous treatments, as determined by the treating physician. The washout periods from prior therapies are intended as follows (windows other than what is listed below should be allowed only after consultation with the Medical Monitor):
 - a. Targeted agents, including small-molecular tyrosine kinase inhibitors: 2 weeks
 - b. Other cytotoxic agents: 3 weeks
 - c. Nitrosoureas: 6 weeks
 - d. Monoclonal antibody immunotherapies (*e.g.*, PD-1, CTLA-4): 6 weeks
 - e. Vaccine-based and/or viral therapy: 3 months
6. On a stable or decreasing dose of dexamethasone for the previous 7 days
7. Able to undergo standard MRI scans with contrast agent before enrollment and after treatment
8. Have age-appropriate functional performance:
 - a. Lansky score ≥ 40 ([Appendix 1](#)) or
 - b. Karnofsky score > 50 ([Appendix 2](#)) or
 - c. Eastern Cooperative Oncology Group (ECOG) score ≤ 2 ([Appendix 3](#))

8. Have adequate bone marrow reserves and liver and kidney function, as assessed by the following laboratory requirements:
 - a. Hemoglobin ≥ 8 g/L
 - b. Absolute lymphocyte count $\geq 500/\text{mm}^3$
 - c. Absolute neutrophil count $\geq 1000/\text{mm}^3$
 - d. Platelets $\geq 100,000/\text{mm}^3$ (untransfused [> 5 days] without growth factors)
 - e. Serum creatinine $\leq 1.5 \times$ upper limit of normal (ULN) for age
 - f. Aspartate transaminase (AST) and alanine transaminase (ALT) $\leq 2.5 \times$ ULN for age
 - g. Total bilirubin $< 1.5 \times$ ULN for age
 - h. International normalized ratio (INR) and activated thromboplastin time within normal institutional limits
9. Male and female subjects of childbearing potential must agree to use a highly reliable method of birth control (expected failure rate $< 1\%$ per year) from the Screening Visit through 28 days after the last dose of study drug. Women of childbearing potential must have a negative pregnancy test at screening.

